9.2. Secondary Efficacy Endpoints and Analyses

Secondary efficacy analyses for the other histological responder endpoints will be analyzed in the ITT and mITT populations using the methods described for the primary efficacy endpoint.

Secondary efficacy analyses of endpoints expressed as percent change or change from Baseline only at Week 26 or only at Week 52 will be analyzed in the ITT analysis set using an analysis of covariance (ANCOVA) model with fixed effects for T2DM status at baseline (Yes, No) and treatment group, and a covariate term for baseline analysis value of response. Least squares (LS) means for the percent change from Baseline by treatment and the associated standard errors, the

LS means for the difference between treatment groups, and the associated two-sided 95% CIs and two-sided p-values, based on t-tests, will be derived from the ANCOVA model.

For secondary endpoints assessed at multiple visits, a linear mixed-effects model for repeated measures (MMRM) may be used. The model will include T2DM status at baseline (Yes, No), treatment group, visit, and treatment-by-visit interaction as the fixed effects, and baseline value as a covariate, and the model will use an unstructured variance-covariance matrix. The point estimates for the least-squares mean of the difference treatment groups at each visit and the corresponding 95% confidence interval and two-sided p-value will be summarized. If convergence problems arise when fitting the model, a spatial power covariance structure will be used as a first step. If the model still has convergence issues, compound symmetry covariance structure will be employed. The Kenward-Roger correction for the denominator degrees of freedom will be applied.

ALT, AST, ALP, and GGT will also be summarized in shift tables of baseline to each visit based on range categories of low (below lower limit of normal [LLN], normal, and high [above upper limit of normal [ULN]]).

The continuous digital pathology variables (qFibrosis, qSteatosis, and Steatosis corrected qFibrosis) will be summarized descriptively with change from baseline being analyzed using MMRM methods. Digital pathology stage/grade variables (qFibrosis – stage, qSteatosis – grade, and Steatosis corrected qFibrosis – stage) will be summarized descriptively with change from baseline being analyzed using ANCOVA methods. The ANCOVA models will include fixed effects for treatment group, T2DM status at baseline (Yes, No), and amount of fibrosis at baseline (F2 or F3), and baseline value as a covariate. Shifts in stage from baseline to each visit will also be presented. The shifts will include decrease in stage, no change in stage, and increase in stage. The shifts will be compared between treatment groups using a CMH-row mean scores test.

Graphical display for selected secondary endpoints will be provided.

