4.3. Sample Size Considerations

The study is powered to test the one-sided (statistical) superiority hypothesis stipulating that a TVB-2640 50-mg dose provides better benefit than placebo based on the primary efficacy endpoint. The study estimated total sample size is approximately 162 randomized subjects (108 on TVB-2640 and 54 on placebo). The sample size was derived using the normal approximation to the binomial distribution, and the estimated power to detect a difference in the primary efficacy response of 20% (TVB-2640 40% and placebo 20% at Week 52) was at least 80% (one-sided test at the 0.05 significance level). A 2-to-1 randomization allocation was assumed (TVB-2640 to placebo), and an anticipated dropout rate of 18.5% was also applied to estimate the final total sample size (N=162).

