7.11. Missing Data

Imputation will only be performed on the primary and selected secondary efficacy endpoints based on histological and MRI-PDFF data. Imputed data will be analyzed using both the ITT and mITT populations.

For the primary efficacy endpoint and secondary efficacy endpoints based on histology, a subject who discontinued treatment prior to Week 42, does not provide a histological assessment on or after Week 42, or who otherwise has missing data will be considered a non-responder. A pre-specified sensitivity analysis of the primary efficacy endpoint will employ the multiple imputation technique.

For the secondary endpoint $\text{MRI-PDFF} \geq 30\%$ responder analysis at Week 26, a subject who discontinued treatment prior to Week 20, does not provide an MRI-PDFF assessment between Week 20 through Week 27, or who otherwise has missing data will be considered a non-responder. For analysis of MRI-PDFF, missing data at Week 26 will be imputed using the last post-baseline observation obtained at least 20 weeks to 27 weeks after the first dose. For the $\text{MRI-PDFF} \geq 30\%$ responder analysis at Week 52, a subject who discontinued treatment prior to Week 42, does not provide an MRI-PDFF assessment after Week 42 or who otherwise has missing data will be considered a non-responder. Missing data at Week 52 will be imputed using the last post-baseline observation obtained at least 42 weeks after the first dose. These missing data techniques will also be applied to $\text{MRI-PDFF} \geq 50\%$ responder analyses.

Additional details are provided in the relevant analysis sections below.

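### Week 52 liver-fat change: the SAP points to a single-visit ANCOVA that makes no use of early leavers' Week 26 scans, leaves the two-visit model optional, and does not settle where Early Termination scans belong

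*SAP*

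**What the plan says.** - **Model.** SAP 9.2 covers one-visit change endpoints with the sentence "Secondary efficacy analyses of endpoints expressed as percent change or change from Baseline only at Week 26 or only at Week 52 will be analyzed", and names an ANCOVA in the ITT set. SAP 7.4 lists MRI-PDFF change at Week 26 and at Week 52 as two endpoints, numbers 13 and 14. The next paragraph of 9.2 permits, but does not require, an MMRM for endpoints measured at several visits. Nothing says which paragraph governs MRI-PDFF.
- **Protocol.** Section 13.2.2, in the MRI-PDFF item itself, commits to an MMRM in addition to the Wilcoxon test and ANCOVA where there are enough post-baseline measurements. SAP 11 does not list the softer wording as a change.
- **Missing Week 52 scans.** SAP 7.11: "Missing data at Week 52 will be imputed using the last post-baseline observation obtained at least 42 weeks after the first dose". The Week 52 responder endpoint also has a non-responder rule. The continuous endpoint has no further rule. The multiple-imputation sensitivity analysis in SAP 9.1.2 is for the co-primary endpoints only.
- **Early Termination scans.** SAP 4.1 waives the scan only for subjects with less than 22 weeks of treatment, apart from hardship; the protocol adds that some sites do no MRI. SAP 7.10 assigns Early Termination data to the nearest scheduled visit or, if that visit already has valid data, to the next available one.
- **Dropout.** SAP 4.3: "an anticipated dropout rate of 18.5% was also applied to estimate the final total sample size (N=162").

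**The concern.** The ITT set is all randomized subjects, but a Week 52 ANCOVA uses only those with a Week 52 value. A subject who leaves at, say, Week 33 has normally been scanned at Week 26. That scan is probably the best available predictor of the missing value, yet the ANCOVA gives it no role.

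An available-case ANCOVA is unbiased only if, given baseline and the model factors, missingness is unrelated to response. Someone whose liver fat is not falling at Week 26 may be more likely to leave. If that tendency differs between arms, the Week 52 difference is biased. Modelling both visits together removes the part of the bias that runs through the Week 26 scan and needs no new data. Leaving the choice of model open also allows it to be made after the results are known.

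**Working it through.** **1. The plan's own figure.** The documents size the trial on the primary endpoint only. SAP 4.3 gives 40% versus 20%, 2:1 allocation, at least 80% power and a "one-sided test at the 0.05 significance level". It adds: "The sample size was derived using the normal approximation to the binomial distribution". With unpooled variances and 88 + 44 = 132 evaluable subjects:
- standard error = √(0.4×0.6/88 + 0.2×0.8/44) = 0.0798
- power = Φ(0.2/0.0798 − 1.645) = 80.6%
- 132/(1 − 0.185) = 162

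The stated 162 is reproduced. Planned dropout is 0.185 × 162 ≈ 30. No sample size or power is given for MRI-PDFF change.

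**2. Who is affected.** The documents do not give dropout timing. If it were even over 52 weeks, 15/52 (29%) of the 30, about 9 subjects, would leave in Weeks 27 to 41. The possible range is 0 to 30.

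**3. Where an Early Termination scan in Weeks 27 to 41 goes under SAP 7.10**, given a valid Week 26 scan:

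| Meaning of scheduled visit | Assignment | Week 52 value? |
|---|---|---|
| MRI visits only (26, 52) | Weeks 27–38: Week 26 is filled, so Week 52. Week 39: a tie, ends at Week 52. Weeks 40–41: Week 52. | Yes, against the Week 42 floor in 7.11 |
| All clinic visits | Weeks 27–32: Week 26 is filled, so Week 39. Weeks 33–41: Week 39. | No |

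Only the second reading agrees with 7.11.

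**4. Precision.** Let n subjects have Week 52 data, m have Week 26 only, and ρ be the Week 26 to Week 52 correlation (assumed). Using the Week 26 scans gives effective n = n/(1 − ρ²m/(n+m)). With n = 132:

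| m | ρ = 0.5 | ρ = 0.7 | ρ = 0.9 |
|---|---|---|---|
| 9 | 134.1 (CI 0.8% narrower) | 136.3 (1.6%) | 139.2 (2.6%) |
| 30 | 138.4 (2.3%) | 145.2 (4.6%) | 155.3 (7.8%) |

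**5. Bias, by simulation.** Assumptions: 108/54 subjects, true effect 0.6 SD, ρ = 0.6 to 0.8, total dropout 18.5% with 29% to 70% of it in the affected window, and log-odds of late dropout rising by 0.7 to 1.5 per SD of worse Week 26 response. SD is the residual SD of Week 52 change. The available-case standard error is √(1/88 + 1/44) ≈ 0.18.

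| Late dropout depends on Week 26 response in | Available-case bias (SD) | Two-visit model bias (SD) |
|---|---|---|
| TVB-2640 arm only | overstates by about 0.02 to 0.13 | at most about 0.01 |
| Placebo arm only | understates by about 0.02 to 0.13 | at most about 0.01 |
| Both arms equally | about 0 | about 0 |
| Neither (random) | about 0; standard error about 1–4% larger than the two-visit model's | about 0 |

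With 29% of dropout in the window, the one-arm bias is about 0.02 to 0.06 SD. With 60% it is about 0.04 to 0.11 SD. Relative to the standard error, the full range is 0.02/0.18 ≈ 0.1 to 0.13/0.18 ≈ 0.7.

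These runs count all 162 subjects. Some sites do no MRI, so the real sample is smaller and its standard error larger.

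**The case against.** The strongest reply is that the plan already contemplates the better model. MRI-PDFF is measured at two post-baseline visits, SAP 9.2 specifies an MMRM with treatment-by-visit and unstructured covariance for such measures, and the protocol commits to one conditionally. So a reader who infers that the SAP firmly assigns the ANCOVA goes too far. What stands is that the wording and the separate listing of endpoints 13 and 14 point to the ANCOVA, and that neither the use nor the rank of the MMRM is fixed.

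A reader might also infer that these subjects have no Week 52 score. The documents do not establish that: an Early Termination scan is expected after 22 weeks of treatment, and one reading of 7.10 places it at Week 52. The defect is the conflict with 7.11.

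Nor is this a completers analysis. Scans from Week 42 count, and SAP 7 uses data regardless of treatment duration.

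The size rests on assumptions, and even dropout timing puts it at the low end. The endpoint is secondary, not powered and without multiplicity control. The companion responder endpoint already counts those who stop treatment before Week 42 as non-responders. All of this stands. It lowers the priority of the point but does not remove it.

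**Conclusion.** The point holds as a modest one. As written, the plan leads to an available-case Week 52 comparison that gives the Week 26 scans of early leavers no role. It does not fix which model is the main one, and its two rules for Early Termination scans before Week 42 conflict.

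The bias is about 0.02 to 0.13 SD, against a standard error of about 0.18, only if late dropout depends on Week 26 response in one arm. A reader might infer that the drug effect would be overstated. The documents do not support that: the direction depends on the arm, and the bias vanishes if the arms behave alike or dropout is random. Correlation, dropout timing and dropout mechanism are all assumptions; only the 18.5% total and the 108/54 split come from the plan. The co-primary histology analyses, with their non-responder rule and multiple-imputation sensitivity analysis, are not touched.

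**What to change.** 1. In SAP 9.2, name one MMRM as the main analysis of endpoints 13 and 14: Weeks 26 and 52, treatment-by-visit, baseline PDFF, the factors already stated there, and unstructured covariance. Report the Week 26 and Week 52 contrasts as the two results.
2. Keep the single-visit ANCOVA as supportive and label it available-case.
3. Reconcile SAP 7.10 with 7.11 by stating that an Early Termination MRI-PDFF scan before Week 42 is not analysed as Week 52. The MMRM alone would not resolve this.

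The cost is SAP wording and one more model, whose form 9.2 already gives. No new data or subjects are needed. The downside is reliance on data being missing at random given the Week 26 scan: dropout driven by what happens after that scan would still bias the result.

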Analysis of the primary efficacy endpoint: The primary efficacy endpoint is the proportion of subjects experiencing either a histological improvement at Week 52 in NAS (ie, ≥ 2 points improvement in NAS with ≥ 1 point improvement in ballooning or inflammation) and without worsening of fibrosis (by NASH CRN fibrosis score), **OR** resolution of steatohepatitis and no worsening of liver fibrosis (by NASH CRN fibrosis score). The treatment groups will be compared based on the primary efficacy endpoint using a one-sided Cochran-Mantel-Haenszel (CMH) test stratified by the randomization stratifications T2DM status (yes or no), region (North America or not North America), and amount of fibrosis (F2 or F3) at the 0.05 significance level (where a higher responder proportion is a better outcome) and will be based on the Intention-to-Treat (ITT) population. The response Clopper-Pearson 90% and 95% confidence intervals (CI) will be derived for each treatment group.

A sensitivity analysis employing a logistic regression will be used to examine the robustness of the CMH results (see details described in the statistical section, below).

A subject who discontinues treatment prior to Week 42, does not provide a histological assessment on or after Week 42, or who otherwise has missing data will be considered a non-responder.

Further sensitivity analysis of the primary efficacy endpoint will employ multiple imputations for binary data. Pertinent details are included in the statistical analysis plan (SAP).

Analysis of the secondary efficacy and pharmacodynamics endpoints: The analysis of the secondary efficacy endpoints will be based on the ITT population. The imputation mechanism used in the analysis of the primary efficacy endpoint will also be adopted where applicable.

The analysis of the secondary efficacy endpoints of a categorical nature will be analyzed in a manner similar to the primary efficacy endpoint.

For the continuous secondary endpoints such as change from Baseline and percent change from Baseline, the Wilcoxon rank-sum test will be used to compare the treatment groups. For the continuous secondary endpoints, an analysis of covariance (ANCOVA) model will also be used with change from

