- MRI-PDFF percent change and change from Baseline at Week 26. This secondary efficacy endpoint will be compared between treatment groups using a one-sided Wilcoxon rank-sum test. An analysis of covariance (ANCOVA) model will also be used with percent change and change from baseline as the dependent variable; treatment group, T2DM status (yes, no), region (North America, not North America), and amount of fibrosis (F2, F3) as factors; and Baseline as a covariate. Least-squares (LS) means and their differences will be estimated from the ANCOVA model and their corresponding 95% CI will be derived. Inferential statistics will be presented for both the ANCOVA model and the Wilcoxon test. For the continuous secondary endpoints with sufficient postbaseline frequency of measurements, a mixed model repeated measure (MMRM) model will also be employed.
- MRI-PDFF percent change and change from Baseline at Week 52. This secondary endpoint will be analyzed similarly to MRI-PDFF percent change and change from Baseline at Week 26, as described above.
- Proportion of subjects with NASH resolution at 52 weeks. Treatment groups will be compared based on this secondary efficacy endpoint using an analysis similar to the primary efficacy endpoint.
- Change from Baseline in ALT, AST, and GGT at Weeks 26 and 52 and at each study visit. This secondary endpoint will be analyzed similarly to MRI-PDFF percent change and change from Baseline at Week 26, as described above.
- Change from Baseline in LDL-C and other lipid levels at Weeks 26 and 52 and at each study visit. This secondary endpoint will be analyzed similarly to MRI-PDFF percent change and change from Baseline at Week 26, as described above.
- Change from Baseline in collagen/fibrous area and fibrosis score, assessed by digital pathology, at Week 52. This secondary endpoint will be analyzed similarly to MRI-PDFF percent change and change from Baseline at Week 26, as described above.
- Changes from Baseline in metabolic parameters, including fasting insulin, fasting glucose, HOMA-IR, adipo-IR, and HbA1c levels at Weeks 26 and 52 and at each study visit. This secondary endpoint will be analyzed similarly to MRI-PDFF percent change and change from Baseline at Week 26, as described above.

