- Change from Baseline in FGF-21, adiponectin, and other NASH biomarker levels at Weeks 26 and 52 and at each study visit. This secondary endpoint will be analyzed similarly to MRI-PDFF percent change and change from Baseline at Week 26, as described above.
- Change from Baseline in FibroScan and CAP score results at Weeks 26 and 52. This secondary endpoint will be analyzed similarly to MRI-PDFF percent change and change from Baseline at Week 26, as described above.

- Change from Baseline in PRO-C3 and other fibrosis biomarkers at Weeks 4, 13, 26, and 52. This secondary endpoint will be analyzed similarly to MRI-PDFF percent change and change from Baseline at Week 26, as described above.
- Change from Baseline in ELF score at Weeks 26 and 52. This secondary endpoint will be analyzed similarly to MRI-PDFF percent change and change from Baseline at Week 26, as described above.

The analysis of the primary and secondary endpoints will be carried out for the ITT analysis set and repeated for the mITT analysis set.

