11. CHANGES TO THE PLANNED ANALYSES

The following changes were made to analyses specified in the protocol. Any additional changes to the planned analyses as detailed in this SAP will be described in the CSR.

- Co-primary objectives and endpoints were added.
- Added 'To evaluate the effect of TVB-2640 50 mg QD compared with matching placebo on resolution of steatohepatitis and no worsening of liver fibrosis (by NASH CRN fibrosis score). Resolution of steatohepatitis is defined as absence of fatty liver disease or isolated or simple steatosis without steatohepatitis and a NAS of 0 or 1 for inflammation, 0 for ballooning, and any value for steatosis at Week 52.' as a secondary objective and endpoint.
- Added 'To evaluate the effect of TVB-2640 50 mg QD compared with matching placebo on histological improvement (decrease) at Week 52 in NAS by ≥ 2 points.' as a secondary objective and endpoint.
- Removed 'To evaluate the effect of TVB-2640 50 mg QD compared with matching placebo on fibrosis as assessed by ≥ 1 stage of fibrosis improvement by NASH CRN score without worsening of NAS (defined as no increase in any component of NAS) at Week 52.' as a secondary objective and endpoint.
- Added proportion of MRI-PDFF $\geq 50\%$ responders, MELD, and Agile3+ endpoints.
- Region (North America or not North America) was removed as an effect in all analyses.

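### SAP 9.2 drops the Protocol's Wilcoxon test and the fibrosis-stage factor without listing either change, and leaves raw-scale models with no protection against skewness or outliers in the continuous secondary endpoints

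*SAP*

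**What the plan says.** **Protocol.** For continuous secondary endpoints the Synopsis (Statistical Methods) states that "the Wilcoxon rank-sum test will be used to compare the treatment groups", and then adds an ANCOVA with treatment, T2DM status, region and fibrosis stage as factors and baseline as covariate. Section 13.2.2 applies this first to MRI-PDFF change and percent change at Week 26: "This secondary efficacy endpoint will be compared between treatment groups using a one-sided Wilcoxon rank-sum test". It again adds the ANCOVA and commits that "Inferential statistics will be presented for both the ANCOVA model and the Wilcoxon test". Liver enzymes, lipids, digital pathology, metabolic parameters, FGF-21 and adiponectin, FibroScan and CAP, PRO-C3 and ELF follow by reference: "This secondary endpoint will be analyzed similarly to MRI-PDFF percent change and change from Baseline at Week 26, as described above".

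**SAP 9.2.** Endpoints assessed only at Week 26 or only at Week 52 are analysed "using an analysis of covariance (ANCOVA) model with fixed effects for T2DM status at baseline (Yes, No) and treatment group", plus the baseline value. For endpoints assessed at several visits, "a linear mixed-effects model for repeated measures (MMRM) may be used". Both work on untransformed change or percent change. The only score-type test concerns digital-pathology stage: "The shifts will be compared between treatment groups using a CMH-row mean scores test". The ANCOVA for those stage and grade variables keeps fibrosis stage as a factor; the general ANCOVA does not.

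**SAP 11.** Under the statement that "The following changes were made to analyses specified in the protocol", the list includes the removal of region from all analyses. It mentions neither the Wilcoxon test nor fibrosis stage.

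**The concern.** There are two separate problems. The first is traceability: an analysis that the Protocol promised for a whole class of endpoints has gone, and a model factor with it, and the section meant to record such changes is silent on both.

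The second is robustness. Triglycerides, insulin, HOMA-IR, adipo-IR, ALT, GGT, FGF-21, PRO-C3 and liver stiffness take only positive values, and a few high values can dominate a mean on the raw scale. The documents give no distributions, so right skew is an assumption, but they leave room for extremes. ALT and AST are excluded only above 5 times ULN. Liver stiffness has an entry floor of 8.5 kPa and no numeric ceiling. Insulin-treated subjects may enrol. The earlier study saw two cases of Grade 3 hypertriglyceridemia (Protocol 5.2). With no rank test and no log scale prespecified, one such value could hide an effect. Any remedy chosen after unblinding would be open to question.

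**Working it through.** **Group sizes.** The documents give no power for any continuous secondary endpoint, so I take the completers implied by the sample-size section (SAP 4.3: 40% vs 20%, one-sided 0.05, 80% power, 2:1, 18.5% dropout). With the unpooled normal approximation:

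placebo n = (1.645 + 0.842)² × (0.20×0.80 + 0.40×0.60/2) / 0.20² = 6.185 × 0.28 / 0.04 = 43.3, so 44.

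Active n = 88, total 132, and 132/0.815 = 162. The plan's figure is reproduced, with 88 and 44 completers.

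**Assumptions not in the documents.** Log-normal values, a true 25% reduction, log-scale correlation of 0.6 between baseline and follow-up, two-sided 0.05. The log-SD is √ln(1 + CV²), so CV 80% gives √ln 1.64 = 0.70. All comparisons are at a single visit.

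**Raw scale against log scale** (ANCOVA power, 4000 simulated trials per row):

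| CV | raw change | percent change | log | log minus raw change |
|---|---|---|---|---|
| 50% | 97% | 97% | 98% | 1 |
| 80% | 68% | 69% | 79% | 11 |
| 100% | 48% | 51% | 64% | 16 |
| 120% | 39% | 40% | 53% | 14 |

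The 1 point at CV 50% is partly a ceiling effect. In a second grid the effect was set so that log-scale ANCOVA has about 80% power, with correlation 0.5 to 0.85. There the shortfall of raw-change ANCOVA was 2 to 3 points at log-SD 0.3, 5 to 8 at 0.5, 10 to 15 at 0.7, and 16 to 24 at 0.9.

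**ANCOVA against the dropped Wilcoxon test** (first setting, no outlier, 2000 trials, each pair from the same run):

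| CV | change: ANCOVA / Wilcoxon | percent change: ANCOVA / Wilcoxon |
|---|---|---|
| 50% | 97% / 89% | 97% / 94% |
| 80% | 66% / 56% | 67% / 67% |
| 100% | 51% / 44% | 50% / 53% |
| 120% | 38% / 34% | 39% / 43% |

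On change, ANCOVA is 4 to 10 points ahead because it uses the baseline value. On percent change the difference is at most 4 points either way. In the second grid ANCOVA on change beat Wilcoxon on change in 10 of 12 log-normal scenarios. With heavy-tailed log residuals (t, 3 df, correlation 0.7) the order reverses, and ANCOVA on change is 7 to 23 points below Wilcoxon.

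**One outlier** (CV 80%, correlation 0.6, one active-arm follow-up value multiplied). Raw-change ANCOVA falls from about 68% to about 56% at 3-fold, 46% at 5-fold and 26% at 10-fold. At 10-fold, Wilcoxon on change is about 50% and log-scale ANCOVA about 65%. The log scale is not full protection: at log-SD 0.3, correlation 0.7, with one treated value at 10 times the median, power is 0% for raw change, 24% for log and 60% for Wilcoxon on change.

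**Type I error.** With no true effect and no outlier, raw-scale ANCOVA rejects in 4.6% to 5.7% of trials. When I added one 10-fold active-arm value under the null at correlation 0.6, its rejection rate fell below 5%.

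**The case against.** A reader might infer that dropping the Wilcoxon test costs 10 to 15 points of power. It does not. That figure is the gap between raw-scale and log-scale ANCOVA at one assumed skewness, and neither document plans a log-scale analysis. Against Wilcoxon on change, keeping ANCOVA usually gains power when there are no outliers.

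A reader might also infer that one outlier makes the raw-scale analysis fail, or that it can create a difference. Failure needs a very large value: at CV 80% a 3-fold value leaves raw ANCOVA at about 56%, still slightly above Wilcoxon on change (about 54%). Creating a false difference is not shown, since type I error is not inflated.

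Other points count on the SAP's side. The Protocol's own ANCOVA was on the raw scale, so the log scale is a new proposal and restores nothing. The quoted ANCOVA sentence covers single-visit endpoints, whereas the skewed analytes are measured at several visits and fall under the MMRM paragraph; the simulations did not test an MMRM. Medians and quartiles are reported (SAP 7), and the liver enzymes get shift tables. These are secondary endpoints, and no primary conclusion depends on them.

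All of this limits the size of the point but does not remove it. SAP 11 leaves additional changes to the CSR, but that does not account for a change already made in SAP 9.2. The wording for multi-visit endpoints also makes matters less definite, because the SAP there commits to no particular test.

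**Conclusion.** The discrepancy is certain from the text: the Protocol requires Wilcoxon and ANCOVA results, SAP 9.2 contains no rank test for continuous endpoints and omits fibrosis stage from its general ANCOVA, and SAP 11 records neither change.

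The size is conditional. Raw-scale ANCOVA has about 1 to 24 points less power than log-scale ANCOVA over the assumed range of skewness, or 11 to 16 points at CV 80% to 120% with correlation 0.6. CV, correlation, effect and log-normality are assumptions, and which analyte has which CV is unknown. The case for the rank test is protection against extreme values and heavy tails, since it gives no general gain in power. The point is worth correcting, but it affects secondary endpoints only.

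**What to change.** In SAP 9.2, before unblinding:

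- Analyse right-skewed positive analytes (triglycerides, insulin, HOMA-IR, adipo-IR, ALT, GGT, FGF-21, PRO-C3, liver stiffness) as log(value) with log(baseline) as covariate, in the ANCOVA or MMRM, and report ratios of geometric means.
- Restore the Protocol's Wilcoxon test as the robustness check, preferably in the van Elteren form stratified by T2DM status and fibrosis stage. Take its sidedness from SAP 7.4, as Protocol 13.4.1 allows.
- Restore fibrosis stage as a factor in the general ANCOVA, or list and justify its removal in SAP 11. If the Wilcoxon test is not restored, list and justify that there as well.
- State definitely which model applies to multi-visit endpoints.

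The cost is SAP wording and a little programming. The drawback is that effects on the logged analytes are read as ratios. If unblinding has already taken place, the Wilcoxon results can still be reported as Protocol-specified, but the log-scale results should be labelled post hoc.
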